### **3.3.5 Subject Disposition**

If a subject permanently and prematurely discontinued the treatment with IP in the LTE study due to the COVID-19 pandemic, identified by the keywords “COVID”, “pandemic” or “corona” in specification of other reason, then the reason for discontinuation of IP in the LTE study is set to “Due to COVID-19 pandemic”.

If a subject withdrew from the LTE study prematurely, the reason for withdrawal is “Other” and the patient’s final status was impacted by the pandemic then the reason for withdrawal from the LTE study is set to “Due to COVID-19 pandemic”.

## **4. ANALYSIS METHODS**

### **4.1 General principles**

#### **4.1.1 Data excluded from analysis**

In the rare event that a site needs to be closed during the course of the study for quality reasons (e.g., suspicion of fraud, non-compliance), all subjects of this site will be excluded from all analyses and summaries. In this situation, the SAP will be amended prior to database lock and details will be added documenting decisions about site closure and data handling (including details of important data to be presented in separate listings).

On 10-Feb-2017, the decision was made to close site [REDACTED] of Study D3461C00004 due to sustained noncompliance with protocol procedures and specifications. This included but was not limited to: failure to follow protocol stipulated inclusion/exclusion criteria, failure to maintain proper documentation in patient source files, and failure to maintain proper principal investigator oversight. The Site, FDA, and IRB have been notified of this site’s closure.

On 12-Jan-2018, the decision was made to close site [REDACTED] (in the LTE study as well as in Study D3461C00005) due to sustained noncompliance with protocol procedures and specifications. This included but was not limited to: lack of adherence to the blinding plan and delegation log by the unblinded pharmacist, and lack of adherence by the site study

coordinator and unblinded pharmacist to their roles and responsibilities for accountability of investigational product including reconstitution and preparation, leading to potential risk of unblinding study data. The Site, FDA, and IRB have been notified of this site's closure.

On 15-Mar-2021, the decision was made by AstraZeneca to exclude data from site [REDACTED] in the LTE study due to non-compliance to ICH E6 (R2) GCP section 8.1 addendum "The sponsor should ensure that the investigator has control of and continuous access to the CRF data reported to the sponsor. The sponsor should not have exclusive control of those data."

On 23 Nov 2021, the decision was made by AstraZeneca to exclude all data from site [REDACTED] in the LTE study since PRA ICON team decided that as the source documentation was destroyed /cannot be recovered as a result of a flood on site.

Therefore, the 20 randomised subjects [REDACTED]  
[REDACTED]  
[REDACTED]  
[REDACTED] ) at these sites and data of subject [REDACTED] who switched to site [REDACTED] after completion of study D3461C00004, will be considered only in repeats of key tables (sensitivity analysis) and key listings (presenting the excluded subjects only) but excluded from all other tables, figures and listings.

Sensitivity analyses are specified in Sections [4.2.1.1](#) and [4.2.2.1](#).

#### **4.1.2 Visit windows**

For visit-based analyses, the variables will be summarised based on the scheduled days with adjusted analysis-defined visit windows. If not stated otherwise, for the Phase 3 feeder studies, only Baseline, Week 24, and Week 52 will be presented in visit-based summaries. The adjusted analysis-defined windows are summarised below:

**Table 2 Visit windows**

Adjusted Defined Windows Visit	Scheduled Study Day	Maximum Windows
Baseline / Day 1	1	Study Day $\leq 1$
Week 24	169	$155 \leq \text{Study Day} \leq 182$
Week 52	365	$351 \leq \text{Study Day} \leq 378$ and LTE Study Day 1
Gap a	N/A	$379 \leq \text{Study Day} \leq \text{LTE Study Day 1}$
Week 56	29 in LTE study	$2 \leq \text{LTE Study Day} \leq 42$
Week 60	57 in LTE study	$43 \leq \text{LTE Study Day} \leq 70$
Week 64	85 in LTE study	$71 \leq \text{LTE Study Days} \leq 98$
...	...	...
Continue in 4-week intervals	Continue in 28-day intervals	Continue in 28-day intervals
...	...	...
Variables to be assessed/measured during follow-up		
Week 208	1092 in LTE study	$1079 \leq \text{LTE Study Days} \leq 1106$
Week 212 (8 weeks post-final dose)	1120 in LTE study	$1107 \leq \text{LTE Study Days} \leq 1134$
Week 216 (12 weeks post-final dose)	1148 in LTE study	$1135 \leq \text{LTE Study Days}$
Variables not to be assessed/measured during follow-up		
Week 208	1092 in LTE study	$1079 \leq \text{LTE Study Day}$

a. This visit window covers longer than expected gaps between the feeder study and the first dose date in the LTE. This visit window will only be used in listings.

For assignment of data to time points using the visit windows, study day will be defined as (Date of assessment – date of first administration of investigational product) +1. Using this definition, the day of first dose of investigational product will be Day 1 and the scheduled visit date of Week 24 will be study day 169 (=168+1), for example. Data captured in the Phase 3 feeder study falling in a visit window after Week 52 [REDACTED] captured in the Phase 3 feeder study falling in Week 52 visit window will not be considered for by-visit summaries. LTE Study Day is defined accordingly as (Date of assessment – date of first administration of investigational product in LTE study) +1. Data assessed at LTE Study Day 1 will be assigned to Week 52 visit window. Data captured in the LTE study after LTE Study Day 1 falling into a visit window before Week 56 will not be considered for by-visit summaries.

If multiple readings are recorded within a single visit window, the following rules will be followed:

- If there are 2 or more observations within the same visit window, then the non-missing one closest to the scheduled visit will be used in the analysis.
- If 2 observations are equidistant from the scheduled visit, then the non-missing observation with the earlier collection date will be used in the analysis.
- If 2 observations are collected on the same day, then the non-missing one with the earlier collection time will be included in the analysis. For observations in the Week 52 visit window, the observation captured in the Phase 3 feeder study is assumed to be earlier than the observation captured in the LTE study even if the collection time is missing or indicating otherwise.
- If 2 observations are collected on the same day and time (if applicable), are captured in the same study and one is reported as done on a scheduled visit and the other as done on an unscheduled visit in the vendor data, then the non-missing one reported as done on a scheduled visit will be included in the analysis.
- If 2 or more antinuclear antibody titre observations are collected on the same day and time, are captured in the same study and at the same visit in the vendor data, then the non-missing one with highest value will be used in the analysis. The following order applies, from lowest to highest: 1:40, 1:80, 1:160, 1:320, 1:640, 1:1280, 1:2560, >1:2560.

If missing week 52 data from a Phase 3 feeder studies have been imputed using last observation carried forward (LOCF; see section 4.1.4) then these data will be considered as non-missing for the rules above. Additionally it will be assumed that the data are closest to the scheduled visit, i.e. the imputed data will always be preferred.

If a visit window does not contain any observations, then the data will remain missing.

For overall analyses not based on any particular study visit, all data will be listed and/or analysed, including any repeat or unscheduled visits, unless otherwise specified.

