**Table 4 Study plan detailing the procedures during Follow-up**

Visit	Follow-up Visit 1 a	Follow-up Visit 2 a
Study Week	8 weeks post-final dose	12 weeks post-final dose
Procedure/Visit Window	±3 D	±3 D
[REDACTED]		
Physical examination, weight		X
Vital signs	X	X
Serum chemistry, haematology, and urinalysis	X	X
Urine pregnancy test in females of childbearing potential	X	X
[REDACTED]		
Assessment of AEs, AESIs, SAEs	X	X
Concomitant medications	X	X

AE = adverse event; AESI = adverse event of special interest; [REDACTED]

[REDACTED] D = day; dsDNA = double-stranded deoxyribonucleic acid; [REDACTED]

[REDACTED] AE = serious adverse event; [REDACTED]

a Follow-up assessments are to be completed when subjects complete the study (eg, early termination or after the treatment period).

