#### 4.2.1 Premature discontinuation of investigational product

Subjects who prematurely discontinue investigational product (see Section 3.9.1) will be asked to return for all regularly scheduled clinic visits. If the subject is unwilling to complete all regularly scheduled clinic visits, the subject should complete the Early Discontinuation Visit (EDV, Week 156) within 4 weeks after the last administration of investigational product, as well as Follow-up Visit 1 and Follow-up Visit 2 (8 and 12 weeks after the last dose of investigational product) unless consent is withdrawn. If the subject is unwilling to continue with any study visits, including EDV, or is willing to continue with only selected study assessments, at a minimum, the following assessments should be completed:

- AEs including AESIs and SAEs
- [REDACTED]
- Serum chemistry, haematology, urinalysis
- Urine for protein, creatinine, and urine-protein-creatinine ratio
- Vital signs
- Physical examination, weight
- [REDACTED]
- [REDACTED]
- Concomitant medications
- Blood test for TB
- Pap smear test (female subjects with an intact cervix only)

If the subject does not agree to do this, they will be asked if they can be followed on a monthly basis via telephone calls. At these calls, they will be asked about AEs/SAEs, lupus symptoms, and lupus medications.

Adverse events will be followed up per Section 6.6.2.

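### SAP Table 2 labels two rows as 8 and 12 weeks after the final dose but fills them by days since the first LTE dose, so the labels are true only for a final dose at LTE Week 152

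*SAP*

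**What the plan says.** SAP 4.1.2, Table 2 ends, for variables measured during follow-up, with rows labelled "Week 212 (8 weeks post-final dose" and "Week 216 (12 weeks post-final dose". The first has a scheduled day of "1120 in LTE study" and a window of LTE Study Days 1107 to 1134. The second has scheduled day 1148 and is open from day 1135.

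The clock is given in the text under the table: "LTE Study Day is defined accordingly as (Date of assessment – date of first administration of investigational product in LTE study) +1". It has no last-dose term, and no readable rule moves these two rows onto one.

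The protocol uses the other clock. Section 4.2.1 asks a subject who stops early and will not keep the regular visits to attend "Follow-up Visit 1 and Follow-up Visit 2 (8 and 12 weeks after the last dose of investigational product". Protocol Table 4 gives ±3 days around each visit and adds in its footnote: "Follow-up assessments are to be completed when subjects complete the study (eg, early termination or after the treatment period".

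Elsewhere the SAP also counts from the last dose. On-treatment values end at last dose + 28 days (SAP 3.1), and adverse events in follow-up run from there to last dose + 84 days (SAP 3.1.1).

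**The concern.** A reader of the tables will take the two rows as the state of the treatment group 8 and 12 weeks after stopping drug. As specified, they show whoever has a record about 160 or 164 weeks after the first LTE dose. Most early stoppers who attend their follow-up visits are absent from these rows. Their off-drug values instead sit in ordinary visit rows without any mark. Some subjects who do appear are not at the labelled time.

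The study's only stated objective is long-term safety, and SAP version 5.0 extended the windows to cover safety follow-up. No by-visit table would then show post-dose vital signs, haematology and chemistry for everyone who stopped.

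**Working it through.** **1. Reproduce the plan's figures.** From the SAP definition, the scheduled LTE day of row week w is 7 × (w − 52) + 1, and the windows run from that day − 14 to + 13 (the first LTE row, Week 56, starts at day 2).

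| Row | Computed day | Printed day | Computed window | Printed window |
|---|---|---|---|---|
| Week 60 | 57 | 57 | 43–70 | 43–70 |
| Week 64 | 85 | 85 | 71–98 | 71–98 |
| Week 208 | 1093 | 1092 | 1079–1106 | 1079–1106 |
| Week 212 | 1121 | 1120 | 1107–1134 | 1107–1134 |
| Week 216 | 1149 | 1148 | from 1135 | from 1135 |

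Week 56 also matches (day 29). The window limits are right; the last three scheduled days are each one low.

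**2. Find the last dose for which the labels are true.** The planned final dose is at LTE Week 152, day 7 × 152 + 1 = 1065. Then 1065 + 56 = 1121 and 1065 + 84 = 1149, the centres of the two rows. Measured from that dose, the windows are 1107 − 1065 = +42 to 1134 − 1065 = +69, and from 1135 − 1065 = +70.

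**3. Map other last doses.** Follow-up Visit 1 is at last dose + 56 days, Visit 2 at + 84.

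| Last LTE dose | LTE day | Visit 1: day, row | Visit 2: day, row |
|---|---|---|---|
| Week 20 | 141 | 197, Week 80 | 225, Week 84 |
| Week 48 | 337 | 393, Week 108 | 421, Week 112 |
| Week 100 | 701 | 757, Week 160 | 785, Week 164 |
| Week 144 | 1009 | 1065, Week 204 | 1093, Week 208 |
| Week 148 | 1037 | 1093, Week 208 | 1121, Week 212 |
| Week 152 | 1065 | 1121, Week 212 | 1149, Week 216 |

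For a Week 148 last dose, the 12-week sample lands in the row labelled 8 weeks. Visit tolerance does not rescue it: ±7 days on the dose and ±3 on the follow-up give days 1111 to 1131, all inside 1107–1134.

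**4. Subjects who stop drug but stay on schedule.** Protocol 4.2.1 asks early stoppers to keep all regular visits, and the documents do not say clearly when these subjects have their follow-up visits. If Visit 2 is held at LTE Week 164 for someone last dosed at Week 20, it enters the 12-week row 164 − 20 = 144 weeks after the last dose.

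**5. Upper bound on size.** Annual dropout is 20% for randomised anifrolumab 300 mg and 30% for placebo and 150 mg (Protocol 8.2, SAP 1.3). At a constant rate, the share stopping before the Week 152 dose is:
- 1 − 0.8^(152/52) = 47.9%
- 1 − 0.7^(152/52) = 64.7%

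Of 575 subjects, that is about 275 if all had the lower rate and 372 if all had the higher. Those last dosed at Week 148 are about 1.5% to 1.9% of early stoppers.

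**6. Rows that receive the displaced values.** Vital signs are scheduled at every treatment visit, so any row can be affected. Chemistry and haematology are scheduled at LTE Weeks 0, 4, 8, 12, 24, 36, 52, 76, 104, 128 and 156 (Protocol Tables 2 and 3). Of the 38 possible early last-dose weeks (0 to 148), Visit 1 falls in one of those weeks for 9 and Visit 2 for 8.

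**The case against.** The strongest reply is that little depends on these rows. The primary AESI and SAE rates use limits set by the last dose. The laboratory and ECG on-treatment shift tables stop at last dose + 28 days. Early stoppers' values stay in the by-visit rows, in the counts of subjects with at least one TELVC, in analyses not tied to a visit, and in listings. All of that stands and keeps this a secondary matter.

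Four stronger readings are tempting, and the documents do not support them:

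- **Only three-year completers enter the rows.** Steps 3 and 4 show other routes in. The labels fail in both directions.
- **Off-drug values contaminate on-treatment summaries.** The SAP does not call its by-visit rows on-treatment, and SAP 4.2 keeps data after discontinuation on purpose. The defect is the label and the lack of a row anchored on last dose.
- **Urinalysis is affected.** SAP 4.2.1.6 gives it shift tables to the last on-treatment value and treatment-emergent changes by parameter, not a by-visit summary.
- **Half to two thirds of follow-up data are lost from these rows.** The dropout figures cannot carry that. Dropout is not the same as stopping drug, and a subject who withdraws consent may have no follow-up visit to misplace. The 20% rate also does not apply to every LTE entrant on 300 mg, since former 150 mg and placebo subjects are among them.

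Most displaced laboratory values fall in weeks without scheduled laboratory visits. There the rule suppressing summaries of fewer than 25 subjects may remove them. That limits mixing in the laboratory tables, but those values would then appear in no by-visit summary.

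**Conclusion.** The point holds as a labelling and assignment error in secondary descriptive tables, and it should be corrected. The two post-final-dose rows match their labels only for a Week 152 final dose. Nearly all early stoppers who attend Follow-up Visits 1 and 2 have those records placed in ordinary visit rows. The outputs affected are the by-visit summaries of vital signs, weight, haematology and chemistry, including laboratory TELVC by visit.

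The 48% and 65% are loose upper bounds. They rest on constant annual dropout, on treating dropout as stopping drug, and on full attendance at both visits.

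The off-by-one in scheduled days 1092, 1120 and 1148 is definite but minor. It bears only on the rule that picks the reading closest to schedule when a window holds several.

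Redacted sections may hold separate rules for other follow-up variables; this cannot be checked.

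**What to change.** In SAP Table 2, assign the two post-final-dose rows by days since each subject's last dose, keeping the table's own spacing:

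- 8 weeks: last dose + 42 to + 69, scheduled + 56.
- 12 weeks: last dose + 70 with a cap, for example + 97 (84 + 13), scheduled + 84.

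Apply this to all records from Follow-up Visits 1 and 2 whenever the subject stopped, and keep those records out of the LTE Study Day windows. State where a follow-up record beyond the cap goes, for example to listings only. Show the rows for all subjects and for completers. Subjects whose final dose is at Week 152 stay in the rows they have now.

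If the sponsor prefers the present assignment, relabel the rows LTE Week 160 and LTE Week 164 and remove the reference to the final dose.

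In either case, correct the scheduled days to 1093, 1121 and 1149. The cost is a SAP table edit and window programming, with no new data.

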### 5.2.9 Clinical laboratory tests

All clinical laboratory tests will be performed in a central clinical laboratory at the times indicated in the Study Plan (Table 2, Table 3, and Table 4).

Urine pregnancy tests will be performed at the site using a dipstick. A serum FSH will be performed at randomisation at the central laboratory in newly postmenopausal females with menses absent for  $\geq 1$  year.

Abnormal safety laboratory results should be repeated as clinically indicated, as soon as possible (preferably within 24 to 48 hours). Additional safety samples may be collected if clinically indicated at the discretion of the Investigator.

Every attempt should be made to redraw any missing safety laboratory test samples, even if the subject has received the investigational product.

The Investigator should make an assessment of the available results with regard to clinically relevant abnormalities. The laboratory results should be signed and dated and retained at the site as source data for laboratory variables. For information on how AEs based on laboratory tests should be recorded and reported, see Section 6.6.

In case a subject shows an aspartate aminotransferase (AST) **or** alanine aminotransferase (ALT)  $\geq 3 \times$  upper limit of normal (ULN) **and** total bilirubin (TBL)  $\geq 2 \times$  ULN [REDACTED] 'Actions Required in Cases of Increases in Liver Biochemistry and Evaluation of Hy's Law' for further instructions.

The following laboratory variables in [Table 5](#) will be measured:

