#### **3.1.2 Vital signs**

The following variables will be explored:

- Pulse (beats per minute)
- Systolic blood pressure (mmHg)
- Diastolic blood pressure (mmHg)
- Respiration rate (breaths per minute)
- Body temperature (°C)

Changes from baseline will be calculated for post-baseline assessments with a corresponding baseline observation.

Where applicable, absolute values will be compared to the reference ranges [REDACTED] and classified as low (below range), normal (within range or on limits), or high (above range). All values (absolute and change) falling outside the reference ranges will be flagged.

Post-baseline values will be classified as treatment-emergent laboratory/vital signs changes (TELVC) according to reference ranges [REDACTED]

For infusion visits, only measurements before the start of investigational product infusion will be considered for by-visit presentations. In the case of multiple measurements before the start of investigational product, the first measurement will be used for by-visit presentations, but all measurements will be considered for the TELVC classification.

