#### **4.2.1.6 Laboratory variables**

Observed values and changes from baseline of laboratory data for haematology, clinical chemistry, and fasting lipid profile will be summarised by visit. The summary statistics presented will be minimum, 1st quartile, median, 3rd quartile, maximum, mean, and SD.

Shift plots (scatter plots) presenting baseline values versus minimum post-baseline values (neutrophils, lymphocytes, monocytes, and haemoglobin only) and maximum post-baseline values (creatinine, creatinine kinase, blood urea nitrogen, alanine aminotransferase, aspartate aminotransferase, bilirubin), respectively, will be provided. A diagonal reference line indicating no change and horizontal and vertical reference lines indicating the limits of the reference ranges will also be displayed on the shift plots.

If any laboratory variables show any unusual features (high or low values or a general shift in the data points) at specific visits, then shift plots of these data may also be produced. This will be discussed and agreed upon during the BDR meeting.

[figure not shown]
For each laboratory parameter with available criteria, the number and percentage of subjects with TELVC values will be summarised by visit. Additionally, the number and percentage of subjects with at least 1 TELVC value will be presented. Percentages will be based on subjects with a measurement at baseline and at least 1 subsequent measurement of the variable (at the respective visit).

[figure not shown]
The number and percentage of subjects with laboratory values below, within, or above the corresponding reference ranges [REDACTED] will be presented as shift tables from baseline to maximum and minimum on-treatment value, respectively.

[figure not shown]
Urinalysis will be summarised as shift tables from baseline to the last on-treatment value for each parameter. Furthermore, the number and percentage of subjects with treatment-emergent changes will be summarised by parameter. Percentages for the summary of treatment-emergent changes will be based on subjects with a measurement at baseline and at least 1 subsequent measurement of the variable.

[figure not shown]
In order to identify potential Hy's Law cases, a shift table of maximum on-treatment total bilirubin against maximum on-treatment ALT, and maximum on-treatment AST expressed as multiples of ULN will be presented.

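### By-visit laboratory TELVC tables can drop an abnormal scheduled result in favour of its repeat, because SAP 4.1.2 selects by distance from the nominal day; three nominal days are also off by one

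*SAP*

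**What the plan says.** **Selection rule (SAP 4.1.2).** Visit-based analyses use one value per window. If there are "2 or more observations within the same visit window, then the non-missing one closest to the scheduled visit will be used". Two further rules favour the earlier sample: "If 2 observations are equidistant from the scheduled visit, then the non-missing observation with the earlier collection date will be used in the analysis", and "If 2 observations are collected on the same day, then the non-missing one with the earlier collection time will be included in the analysis". Scheduled status decides only when two values share date, time and study. Whether a value is abnormal plays no part.

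**Repeats (Protocol 5.2.9).** "Abnormal safety laboratory results should be repeated as clinically indicated, as soon as possible (preferably within 24 to 48 hours".

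**Outputs (SAP 4.2.1.6).** For laboratory parameters with criteria, "the number and percentage of subjects with TELVC values will be summarised by visit". The same section also plans a count of subjects with one or more TELVC, shift tables and plots based on minimum and maximum values, and potential Hy's Law outputs based on maxima.

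**Protection elsewhere.** SAP 4.1.2 adds: "For overall analyses not based on any particular study visit, all data will be listed and/or analysed, including any repeat or unscheduled visits". For several pre-infusion vital-sign readings, SAP 3.1.2 takes the first for by-visit tables, "but all measurements will be considered for the TELVC classification". Laboratory variables have no matching sentence.

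**The concern.** The rule looks neutral because it ignores the result. The second sample, however, is often taken because the first was abnormal. Where that repeat lies nearer the nominal day, the by-visit table shows the repeat and drops the value that prompted it. A repeat of an extreme value tends to lie nearer normal, so the by-visit TELVC count tends to fall.

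These tables show how laboratory safety evolves over time. In Years 2 and 3, chemistry, haematology and urinalysis are scheduled only about every six months (Protocol Table 3), so each time point carries weight. SAP Table 2 also supplies the nominal days from which closeness is measured, so an error there can change which value is chosen.

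**Working it through.** **Inputs from the documents**
- Selection, tie and same-day rules: SAP 4.1.2.
- Preferred repeat lag *k*: 1 to 2 days (Protocol 5.2.9).
- Visit tolerance: ±7 days on treatment (Protocol Tables 2 and 3), ±3 days in follow-up (Protocol Table 4).
- LTE windows: 28 days. Week 60 is days 43 to 70 around day 57, which is −14 to +13.

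**Inputs that must be assumed:** the distribution of actual visit days, the share of abnormal values repeated, and the share of repeats that are normal.

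**Step 1. When the repeat wins.** Let the scheduled sample lie *d* days from nominal and the repeat *d + k*. The repeat is chosen only if |d + k| < |d|, that is, d < −k/2. A visit at +7 with a 2-day repeat ends at +9, still inside +13, so both values share a window.

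Example: the LTE Week 24 visit has nominal LTE day 7 × 24 + 1 = 169. An abnormal sample on day 165 with a repeat on day 167 gives distances 4 and 2, so the repeat is used. A sample on day 168 with a repeat on day 170 is a tie, so the first is kept. A sample on or after day 169 is always kept.

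**Step 2. Share of repeated abnormal values displaced**

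| Assumed visit timing | k = 1 | k = 2 |
|---|---|---|
| All on the nominal day | 0% | 0% |
| Uniform, ±7 days | 7/15 = 47% | 6/15 = 40% |
| Uniform, ±3 days (follow-up) | 3/7 = 43% | 2/7 = 29% |
| Normal within ±7, SD 3 | 43% | 31% |
| Normal within ±7, SD 2 | 40% | 22% |
| Normal within ±7, SD 1 | 30% | 6% |
| SD 3, running 2 days late | 21% | 12% |
| SD 3, running 2 days early | 68% | 55% |

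A 7-day lag gives 4/15 = 27% (uniform ±7) or 12% (SD 3).

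**Step 3. Effect on by-visit TELVC counts.** Relative loss = share displaced × share repeated × share of repeats that are normal. A simulation with normally distributed values repeated only a share of the abnormal ones. It assumed within-subject correlation 0.5 to 0.85 and true prevalence 2% or 5%, and 44% to 83% of repeats came back normal. With 50% to 100% repeated and 20% to 47% displaced:
- low: 0.20 × 0.50 × 0.44 = 0.044, about 4%;
- high: 0.467 × 1.00 × 0.83 = 0.39, about 39%.

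These are illustrations, not bounds. With 6% displaced (SD 1, 2-day lag), 0.06 × 0.50 × 0.44 = 0.013, about 1%. With every visit on its nominal day the loss is zero.

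**Step 4. Effect on by-visit means.** In the same simulation the mean moves 0.001 to 0.024 SD towards normal, which is negligible.

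**Step 5. Nominal days.** The SAP convention is 7 × week + 1. It reproduces the SAP Table 2 entries 169 and 365 for feeder Weeks 24 and 52, and 29, 57 and 85 for LTE Weeks 4, 8 and 12. Continuing in 28-day steps:
- Week 208: 85 + 36 × 28 = 1093; listed 1092.
- Week 212: 1093 + 28 = 1121; listed 1120.
- Week 216: 1121 + 28 = 1149; listed 1148.

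The Week 208 window, 1079 to 1106, is −14 to +13 around 1093, the same pattern as Week 60. Measured from the listed day, displacement at Week 208 under uniform timing is 6/15 = 40% (1-day lag) or 5/15 = 33% (2-day lag). The slip therefore does not worsen displacement there, but it is still the wrong reference day.

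**The case against.** The case on the other side is substantial, and much of it stands.

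- **Frequency.** A reader might infer that abnormal values are often replaced. The documents do not support that. They give no actual visit timing, repeats are only as clinically indicated, and the one-to-two-day timing is a preference. It is not stated whether that clock starts at the draw or at the report. With central testing the lag from the draw may be longer, which lowers the share.
- **Direction.** A reader might infer that selection runs strictly one way. It does not. Protocol 5.2.9 allows discretionary extra samples, Protocol 5.2 calls for local monitoring when background therapy changes, and Protocol 4.3 allows unscheduled visits. Such a sample can be abnormal and displace a normal scheduled value. The tendency towards normal applies to repeats prompted by abnormal results.
- **Vital signs.** SAP 3.1.2 is not a precedent for taking the worst value in a window. It counts all readings, and vital-sign TELVC is tabulated by year (SAP 4.2.1.2). It shows only that the SAP addressed multiple readings there and not for laboratory data.
- **Ambiguity.** The percentage base in SAP 4.2.1.6 refers to subjects with one or more later measurements at the visit. If every value in the window is classified, the TELVC effect disappears. SAP 4.1.2 governs visit-based analyses, so the single-value reading is more natural, but two programmers could differ.
- **Worst value in the window.** This would bring the opposite bias for subjects tested more often, so it is not the obvious remedy.

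What remains is that an unscheduled repeat can overwrite the abnormal scheduled value that prompted it, and no laboratory rule prevents this.

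**Conclusion.** The point holds as a limited defect in the by-visit laboratory TELVC tables. Displacement requires a scheduled sample early by more than half the repeat lag. Among repeated abnormal values the share displaced is 0% to about 47%, and higher only if visits run systematically early. The resulting loss in by-visit counts cannot be fixed from the documents, because visit timing, repeat rates and normalisation rates are not given and the TELVC limits are redacted.

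Two stronger readings should be set aside. By-visit means are not materially biased (at most 0.024 SD under the assumptions tried). Nor do the documents show that group comparisons are distorted in general: an equal proportional loss shrinks an absolute difference but leaves the ratio unchanged, and no formal comparisons are planned (SAP 1.3).

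The count of subjects with one or more TELVC, the minimum and maximum shifts, the Hy's Law outputs and the primary AESI and SAE analyses are unaffected. A Week 52 value taken on LTE Day 1 cannot be displaced by a later LTE repeat, which falls in the Week 56 window.

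The Table 2 slip stands without any assumption: the three listed days contradict the SAP's own convention by one day.

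**What to change.** 1. In SAP 4.1.2, for by-visit laboratory summaries and TELVC, use the scheduled-visit value and take an unscheduled value only if the scheduled one is missing. The distance rule can still choose among values of the same status.
2. In SAP 4.2.1.6, state that this value defines by-visit laboratory TELVC, and that all values, including repeats, still count towards the overall one-or-more-TELVC figure.
3. In SAP Table 2, correct the scheduled days for Weeks 208, 212 and 216 to 1093, 1121 and 1149, including both Week 208 rows. The windows can stay.

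This reduces displacement of an abnormal scheduled value by its later repeat to 0% and settles the ambiguity. The cost is a few sentences and a small programming change. The scheduled or unscheduled flag is already needed for the existing same-time rule. The downside is small: where both values exist, the scheduled one may lie slightly further from the nominal day.
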